6.3.3.2 HAL and pedHAL

The Haemophilia Activities List (HAL, in patients ≥ 18 years of age) and pediatric HAL (pedHAL, in patients < 18 years of age) questionnaires assess subjective functional ability to perform activities of daily living. Overall score, component scores, domain scores, and their changes will be summarized by scheduled visits.

6.3.3.3 EQ-5D-5L

The EQ-5D-5L is a standardized instrument for use as a measure of QOL outcome. Index value and visual analogue scale (VAS) score and their changes from baseline will be summarized. Numbers and percentages of patient by level and dichotomized level (1 = no problems, 2 to 5 = “problems”) of each dimension will be reported.

6.3.3.4 Haemo-QOL

The Haemo-QOL will be provided to patients < 17 years of age. The change from baseline in total score of Haemo-QOL will be analyzed using an analysis of covariance (ANCOVA) model with fixed effects of treatment arm and randomization strata of the number of bleeding episodes in the 6 months prior to study entry (≤ 10 vs > 10), baseline Haemo-QOL total score as covariate. Domain scores for Haemo-QOL and their changes from baseline will be summarized descriptively. Only the descriptive statistics will be provided if ANCOVA model does not converge due to the small sample size.

6.3.3.5 Number of target joint bleeding episodes

A target joint is defined as a joint where 3 more spontaneous bleeding episodes in a single joint within a consecutive 6-month period have occurred. The target joints are identified at baseline and their bleeding episodes are captured and monitored during the study. An exploratory analysis of the number of target joint bleeding episodes may be performed using the same negative binominal model as the primary analysis.

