### 5. SELECTION AND WITHDRAWAL OF PATIENTS

#### 5.1. Inclusion Criteria

Each patient must meet all of the following inclusion criteria to be eligible for enrollment in the study:

1. Males  $\geq 12$  years of age.
2. Severe hemophilia A or B with inhibitors evidenced by:
  - a. A central laboratory measurement or documented medical record evidence of FVIII  $< 1\%$  or FIX level  $\leq 2\%$  at Screening.
  - b. On-demand use of BPAs to manage bleeding episodes for at least the last 6 months prior to Screening, and meet one of the following Nijmegen-modified Bethesda assay results criteria:
    - Inhibitor titer of  $\geq 0.6$  BU/mL at Screening, or
    - Inhibitor titer of  $< 0.6$  BU/mL at Screening with medical record evidence of 2 consecutive titers  $\geq 0.6$  BU/mL, or
    - Inhibitor titer of  $< 0.6$  BU/mL at Screening with medical record evidence of anamnestic response
3. A minimum of 6 bleeding episodes requiring BPA treatment within the last 6 months prior to Screening.

- 
4. Willing and able to comply with the study requirements and to provide written informed consent and assent in the case of patients under the age of legal consent, per local and national requirements.

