## 7.2. Efficacy Assessments

### *Bleeding Episode Definitions*

A bleeding episode is defined as any occurrence of hemorrhage that requires administration of factor concentrates or BPA infusion, eg, hemarthrosis, muscle, or mucosal bleeding. Since bleeding episodes are recorded as an efficacy assessment of fitusiran, these will not be treated as AEs unless they meet any of the SAE criteria listed in Section 7.5.6.1.

The definition of bleeding episode types described below is based on consensus opinion of International Society on Thrombosis and Haemostasis (ISTH) as reflected in a recent publication.[12]

The start time of a bleeding episode will be considered the time at which symptoms of a bleeding episode first develop. Bleeding or any symptoms of bleeding at the same location that occurs within 72 hours of the last injection used to treat a bleeding episode at that location will be considered a part of the original bleeding event, and will count as one bleeding episode towards the ABR. Any bleeding symptoms that begin more than 72 hours from the last injection used to treat a bleeding episode at that location will constitute a new bleeding event.

A spontaneous bleeding episode is a bleeding event that occurs for no apparent or known reason, particularly into the joints, muscles, and soft tissues.

A joint bleeding episode is characterized by an unusual sensation in the joint (“aura”) in combination with 1) increasing swelling or warmth over the skin over the joint, 2) increasing pain, or 3) progressive loss of range of motion or difficulty in using the limb as compared with baseline.

A muscle bleed may be characterized by pain, swelling and loss of movement over the affected muscle group.

A target joint is defined as a joint where 3 or more spontaneous bleeding episodes in a single joint within a consecutive 6-month period has occurred; where there have been  $\leq 2$  bleeding episodes in the joint within a consecutive 12-month period the joint is no longer considered a target joint.

---

A traumatic bleeding episode is one that is caused by a known injury or trauma. Bleeding episodes sustained during sports and recreation will be counted as traumatic bleeding episodes, but patients will be asked to indicate in the eDiary that the event occurred during such activities. Training will be provided on this and other aspects of eDiary use (see Section 7.2.1).

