4 PATIENT POPULATION

The populations (analysis sets) are defined as follows:

- Intent-to-treat (ITT) Analysis Set: All randomized patients. All by-treatment analyses based on the ITT analysis set will be performed according to the randomized treatment arm. Efficacy Analyses will be conducted using the ITT Analysis Set unless otherwise specified.
- Safety Analysis Set: All patients who received at least 1 dose of study drug or were randomized to on-demand arm. All by-treatment analyses based on the safety analysis set will be according to the actual treatment received. Safety Analyses will be conducted using the Safety Analysis Set unless otherwise specified.
- Per-protocol Analysis Set: All patients in the ITT set who do not have protocol deviations in the following categories:
 - Failure to meet key Eligibility criteria, which will be identified prior to database lock
 - Actual treatment differs from IRS treatment assignment
 - Prophylactic use of BPA
 - Other protocol deviations that might significantly affect the completeness, accuracy, and/or reliability of the bleeding data.

The major or critical deviations to be considered are as follows.

- The subject is not male and/or is younger than 12 years, but the subject was randomized.
- The subject does not have severe hemophilia A or B with inhibitors as evidence by:
 - A laboratory FVIII level $<1\%$ or FIX level $\leq 2\%$ at Screening.
 - On-demand use of bypassing agents to manage bleeding episodes for at least the last 6 months prior to Screening, or meeting one of the following Nijmegen-modified Bethesda assay results criteria:
 - Inhibitor titer of ≥ 0.6 BU/mL at Screening,
 - Inhibitor titer of <0.6 BU/mL at Screening with medical record evidence of 2 consecutive titers ≥ 0.6 BU/mL,
 - Inhibitor titer of <0.6 BU/mL at Screening with medical record evidence of anamnestic response, but the subject was randomized.
- The subject does not have a minimum of 6 bleeding episodes requiring bypassing agent treatment within the last 6 months prior to Screening, but the subject was randomized.
- The subject has known co-existing bleeding disorders other than hemophilia A or B, but the subject was randomized.

- The subject currently uses bypassing agents as regularly administered prophylaxis designed to prevent spontaneous bleeding episodes, but subject was randomized.
 - The subject's actual treatment differs from randomization group.

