5 GENERAL STATISTICAL METHODS

5.1 Sample Size Justification

Assuming a mean ABR of 18 with standard deviation (SD) = 14 in the on-demand arm (patients randomized to receive on-demand bypassing agents) and a mean ABR of no more than 4 with SD = 6 in the fitusiran treatment arm (patients randomized to receive fitusiran) in either the efficacy period or treatment period, with a sample size of 14 evaluable patients in on-demand arm and approximately 28 evaluable patients in the fitusiran treatment arm, it is projected that the study will have greater than 90% power for testing treatment difference in mean ABRs. This power estimation was based on negative binomial regression model with a 2-sided type I error rate of 0.05.

The planned sample size is 54 randomized patients assuming a 20% drop-out rate.

In the China Addendum #1 to protocol amendment 2, it specifies that before any Chinese patients are randomized to receive 80 mg of fitusiran subcutaneous (SC) treatment, three (3) subjects in China will be enrolled into a China specific non-randomized fitusiran treatment arm to receive fitusiran as a SC injection administered every 4 weeks, with initial starting dose of 50 mg SC. After the observation period for these 3 patients is completed and dose escalation is authorized by the Sponsor, the 3 patients will undergo dose escalation to receive 80 mg of fitusiran as a SC injection every 4 weeks. These 3 patients will not be included in the ITT Set for the efficacy analyses but will be included in the Safety Set for the safety analyses. Their efficacy data will be included in separate listings.

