6.3.1 Primary Endpoint

6.3.1.1 Primary Efficacy Analysis based on On-Treatment Strategy

The primary objective of this study is to assess the efficacy of fitusiran in the prevention or reduction of bleeding. Including bleeding events in the period of intercurrent events such as use of prophylactic medication or surgery or after fitusiran treatment discontinuation could significantly bias fitusiran effect and make the comparisons difficult to interpret. The on-treatment strategy is considered of greatest relevance in assessing this primary objective (ICH E9 (R1), 2018). The primary efficacy analysis population will be the ITT Analysis Set as defined in [Section 4](#).

Global Protocol

The number of bleeding episodes will be annualized for each patient using the following formula:

$$\text{Annualized bleeding rate (ABR)} = \frac{\text{total number of bleeding episodes}}{\text{total number of days in the respective period}} \times 365.25.$$

The primary efficacy analysis will include all bleeding episodes occurring in the efficacy period.

Let λ_F represent the ABR for fitusiran arm and λ_O represent the ABR for on-demand arm. The null and alternative hypotheses of the primary analysis, respectively, can be written as follows:

$$H_0: \frac{\lambda_F}{\lambda_O} = 1 \qquad H_A: \frac{\lambda_F}{\lambda_O} \neq 1$$

An estimated ABR ratio $\frac{\lambda_F}{\lambda_O} < 1$ and two-sided p-value < 0.05 from the significance test will lead to the rejection of H_0 in favor of H_A ; it will be concluded that prophylactic use of fitusiran reduces the frequency of bleeding episodes compared to the on-demand therapy.

The ABR ratio λ_F/λ_O will be estimated using a negative binomial model:

$$\log(\text{number of bleeding episodes}) = \beta_0 + \beta_1 \cdot \text{Treatment} + \beta_2 \cdot \text{ABR}_0 + \log(\text{duration}).$$

The number of bleeding episodes is the response variable. The treatment arm and the randomization strata of number of bleeding episodes in the 6 months prior to study entry (ABR_0) are treated as fixed effects. The logarithm of the duration (in years) that each patient spends in the efficacy period matching the bleeding episode data being analyzed is included as an offset variable to account for unequal follow-up time due to early withdrawal, surgery, etc.

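### If the optional target-joint analysis is run with the unmodified primary model, it loses precision by ignoring the number of target joints each patient had at baseline

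*SAP*

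**What the plan says.** SAP 6.3.3.5 makes the analysis optional: "An exploratory analysis of the number of target joint bleeding episodes may be performed using the same negative binominal model as the primary analysis". The sentence before it fixes the joints in advance: "The target joints are identified at baseline and their bleeding episodes are captured and monitored during the study".

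The model it points to is in SAP 6.3.1.1. The fixed effects are "The treatment arm and the randomization strata of number of bleeding episodes in the 6 months prior to study entry". The offset is "The logarithm of the duration (in years) that each patient spends in the efficacy period matching the bleeding episode data being analyzed". Neither refers to target joints.

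SAP Section 4 sets the default population: "Efficacy Analyses will be conducted using the ITT Analysis Set unless otherwise specified". Section 6.3.3.5 specifies nothing else.

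Eligibility (Protocol 5.1) requires "A minimum of 6 bleeding episodes requiring BPA treatment within the last 6 months prior to Screening", at any site. The target-joint definition (Protocol 7.2), quoted here up to its closing verb, is narrower: "A target joint is defined as a joint where 3 or more spontaneous bleeding episodes in a single joint within a consecutive 6-month period has". An eligible patient can therefore have no target joint.

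The endpoint is listed as exploratory (Protocol 3.3, SAP 3.2.1) and is outside the testing hierarchy (SAP 5.7).

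**The concern.** Once target joints are fixed at baseline, a patient with none cannot have the event, yet adds a zero with full follow-up time. Among the others, the opportunity to bleed grows with the number of target joints, and the model treats them as equally exposed. Both features enter the model as unexplained overdispersion and widen the confidence interval for the rate ratio.

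The SAP does use the endpoint's own baseline elsewhere: for Haem-A-QoL (6.3.2.4), Haemo-QOL (6.3.3.4), AT lowering (6.4.1) and peak thrombin (6.4.2). It also plans a zero-inflated model for the main bleeding analyses (6.3.1.2). Neither step is taken here, where the zeros are built in. Target joints are also absent from the baseline disease characteristics in SAP 6.2, so no specified table would show how they fell between 36 and 18 patients.

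At stake are the precision and readability of one exploratory result: a rate per randomised patient, not a rate per target joint.

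**Working it through.** **Inputs from the documents.** Efficacy period Day 29 to Day 246: 246 − 29 + 1 = 218 days, so t = 218/365.25 = 0.597 years. Mean ABR 18 (SD 14) on demand and at most 4 (SD 6) on fitusiran. Evaluable patients 14 and 28; randomised 54, that is 18 and 36.

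**The plan's own figure.** With k = (SD² − mean/t)/mean²:
- on-demand: (196 − 30.16)/324 = 0.51
- fitusiran: (36 − 6.70)/16 = 1.83

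Var(log rate ratio) = (1/(18t) + 0.51)/14 + (1/(4t) + 1.83)/28, so SE = 0.352. With |log(4/18)| = 1.504, power = Φ(1.504/0.352 − 1.96) = 99.0%. A weighted common k gives 95.4%, and the larger k in both arms gives 89.7%. This agrees with the stated power of more than 90%. For drop-out, 42/0.8 = 52.5, hence 53, and 54 at 2:1. The plan states no precision for the target-joint analysis.

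**As written against modified.** Let p0 be the share with no target joint, T the number among the rest, r the bleeds per target joint per year in an arm, and k its dispersion.
- As written (all patients, log-time offset), per arm: V = (m₂ − m²)/(n m²), with m = (1 − p0)·E[T]·rt and m₂ = (1 − p0)·E[T²]·(rt)²·(1 + k) + m.
- Modified (T ≥ 1, offset log(T × time)), per arm: V = 1/[n(1 − p0)·Σ P(T)·μ_T/(1 + kμ_T)], with μ_T = T·rt.

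*Worked case.* Assume p0 = 20%, T = 1/2/3 in 50/30/20%, and r = 5 on demand; take the rate ratio 4/18 and k = 0.51/1.83 from the plan. E[T] = 1.7, E[T²] = 3.5.
- As written: 0.0851 (on-demand) + 0.1220 (fitusiran) = 0.2072; SE 0.455.
- Modified: 0.0512 + 0.0987 = 0.1500; SE 0.387.
- Variance ratio 1.38, so 1 − 1/1.38 = 28% of the information is lost.

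*Range over assumed distributions* (variance as written ÷ modified):

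| No target joint | Number among the rest | k = 0.51/1.83 | k = 0.3/0.3 |
|---|---|---|---|
| 0% | all 1 | 1.00 | 1.00 |
| 0% | 1/2/3 in 50/30/20% | 1.24 | 1.32 |
| 20% | all 1 | 1.12 | 1.19 |
| 20% | 1/2/3 in 50/30/20% | 1.38 | 1.58 |
| 30% | 1/2/3 in 50/30/20% | 1.45 | 1.71 |
| 50% | 1/2/3 in 50/30/20% | 1.59 | 1.98 |
| 50% | 1/2/3 in 34/33/33% | 1.57 | 2.00 |

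A ratio of 2.00 is a 50% loss; 1.59 is 37%.

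**Simulation from joint-level bleeding.** 36 v 18 patients, 10 scenarios, 600 trials each. Assumptions: six candidate joints carrying 75% of bleeds with varying spread, at least 6 prior bleeds per patient, and a target joint defined by at least 3 baseline bleeds. This left 8% to 33% of patients with none, and 1.3 to 1.7 target joints per affected patient.
- Median rate ratio 0.21 to 0.23 under every model, against a true 0.222: no material bias.
- Variance ratio from the squared model SE: 1.09 to 1.68 with the per-joint offset. The as-written SE is √1.09 to √1.68, about 4% to 30% larger, and about 8% to 40% of the information is lost.
- With the log baseline target-joint bleed count as a covariate: 1.22 to 1.67. Restriction alone: 1.12 to 1.26.

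**Simulation from assumed counts.** Reduction in the variance of the log rate ratio after the change to the per-joint analysis:
- 40/30/20/10% with 0/1/2/3 joints, k = 0.51 in both arms, 4 v 1.5 bleeds per joint-year: 38% to 47% over repeated runs.
- 20/40/30/10% with the plan's dispersions and rate ratio: about 27%.
- 90% with exactly one joint: about 9%.

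**False positives.** With no drug effect, the as-written model rejected about 4% of the time. The restricted per-joint model with a plain Wald test rejected about 7% to 8%.

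**The case against.** The strongest reply is that the plan's version answers a legitimate question. The endpoint is the number of target-joint bleeds. On the ITT set, the primary model gives the patient-level rate ratio in the randomised population, consistent with the spontaneous and joint bleeding endpoints. The per-joint version describes a different population and, as an offset, assumes proportionality. That stands, and it is why the all-ITT version should be kept. The prior-bleed stratum also recovers some of the baseline information.

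Three stronger readings are tempting and are not supported.
- *That a chance imbalance in target joints would be read as a drug effect.* Imbalance does drive noise: in the 40/30/20/10% scenario the between-arm ratio of mean target joints ran from 0.67 to 1.69 (5th to 95th percentile) and correlated 0.66 with the as-written log rate ratio. But this is a pre-randomisation covariate, so its variation is already in the standard error. The estimate is unbiased and false positives are about 4%.
- *That much of the precision or power is certainly lost.* In that scenario nominal power rises from 47% to about 75% to 78%. The scenario assumes 40% of patients with no target joint, the on-demand dispersion in both arms and a rate ratio of 1.5/4 = 0.375 instead of the plan's 0.222. Part of the rise is the Wald test's inflated size. In the joint-level simulation the as-written model already has 83.5% to 99.8% power.
- *That the plan commits to this analysis.* It says only that it may be done.

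**Conclusion.** The point holds as an inexpensive refinement. As written, the optional analysis gives patients without a target joint full exposure and leaves out a baseline count that the SAP says is identified. The estimate stays unbiased; the loss is precision and a per-joint interpretation.

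The loss runs from almost none, when nearly everyone has one target joint, to about half the information, when about 40% to 50% have none and the rest have one to three. The upper end also needs low dispersion: with the dispersions implied by the plan's SDs, the most in the table is 37%. All of this rests on assumed distributions, because the documents give none. No primary or hierarchical secondary conclusion changes.

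**What to change.** Add to SAP 6.3.3.5, before database lock: if the analysis is performed, it includes patients with at least one target joint at baseline, in a negative binomial model with arm, prior-bleed stratum and log(number of baseline target joints) as a covariate, with log time as the offset. An offset of log(years × number of target joints) is the alternative. Test by a permutation or likelihood-ratio test instead of a plain Wald test. Tabulate the number of target joints by arm. Retain the all-ITT model as a supportive patient-level rate.

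The cost is a few lines of text and one table; no new data are needed. Because the count is fixed before treatment, the restriction keeps the randomised comparison. The downsides are that the estimate applies only to patients with a target joint and that the offset version assumes bleeds proportional to the number of joints, which the covariate version relaxes. Writing it down in advance also removes a later choice of model.

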6.3.3.6 HJHS

Joint health status will be assessed via the HJHS, as administered by a healthcare professional trained in the use of anthropometric measures. Response will be summarized. If the joint score is evaluated with 2 weeks after a joint or adjacent muscle bleeding episode or a surgery is performed on a joint and the joint score is evaluated from start date of surgery to the end of perioperative procedure period + 7 days, then the data for that joint will be excluded. A sensitivity analysis excluding the non-evaluable results will be performed.

6.3.3.7 Annualized weight-adjusted consumption of BPA

BPA dose will be recorded by the patient in the eDiary and reviewed by the Investigator (and Sponsor or delegate) for the study duration to assess on-demand BPA usage, as treatment of breakthrough bleeding episodes. Weight-adjusted BPA usage will be calculated programmatically.

The annualized weight-adjusted BPA consumption, number of BPA injections per bleed/per subject, weight adjusted total dose per bleed/per subject, and results of patient-reported evaluation of effectiveness of treatment for each bleed (excellent, good, moderate or none) as assessed by both patient and caregiver (Blanchette, 2014) will be summarized by study period. BPA consumption during Day 1 to Day 8 period under 'standard BPA regimen' will be summarized as appropriate. Day 1 to Day 8 period is from Day 1 to the earlier of Day 8 and the last day of bleeding follow up. Additional summary will be provided by bleed location, causality and severity. The compliance to the bleed management guideline will be summarized after Day 8 to the end of study.

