#### **6.3.1.2. Bleeding Episode Management Recommendations for Patients in the Fitusiran Treatment Arm**

Given the mechanism of action and pharmacodynamics profile of fitusiran, the BPA dose necessary to safely and effectively treat breakthrough bleeding episodes in patients receiving fitusiran (fitusiran treatment arm) will be lower than standardly prescribed. This is supported by data from the Phase 1 study in which bleed events were managed with factor or BPA, as well as additional modeling and ex vivo spiking data. More detailed information on the clinical experience in bleeding episode management in Phase 1 and Phase 1/2 fitusiran studies, as well as supportive nonclinical studies is provided in the Investigator's Brochure.

After administration of fitusiran, AT lowering will be progressing toward therapeutic levels. As quickly as 7 days after the initial fitusiran dose, the majority of patients will have AT levels at or below 60% residual activity. By 14 days after dosing, it is expected that 94% of patients will have AT lowering of >50%, with a median value of 66.8 %. Based on these AT kinetics, it is

---

recommended that patients continue with their standard BPA regimens for the first 7 days following initiation of fitusiran dosing, with institution of the protocol-specific bleed management guidelines with reduced BPA at Day 8 and beyond (Table 4).

Patients on fitusiran will be provided a written bleed management plan with appropriate dosing of BPA for use during Day 1 through 7, as well as a bleed management plan with dosing for Day 8 and beyond. Thereafter the bleed management plan will be reviewed and updated at monthly visits, and new written plans provided to the patient if dosing changes.

Importantly, during the treatment period, patients should not use BPA or other hemostatic agents as prophylaxis for bleeding episode prevention, including doses related to anticipated hemostatic challenges such as physical activity. For prophylaxis of bleeding episodes in patients who require operative procedures (see Section 6.6).

**Bleed Management Guidelines Day 1 to Day 7:** Patients should be instructed to call the site prior to administering factor or BPA. Patients should continue with their standard BPA regimens.

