**Bleed Management Guidelines Day 8 and Beyond:**

When a patient experiences symptoms that may be consistent with bleeding episodes, the following steps should be followed:

1. Patient should be instructed to call the study center to discuss symptoms to determine whether or not they are consistent with a bleeding event and to discuss the appropriate factor/BPA dose to use. This interaction between patient and Investigator is recommended prior to the administration of each dose of factor or BPA. Confirmation of bleeds at the study center prior to treatment may be considered. Such visits should capture assessments per Section 6.4 and Table 2.
2. If a determination is made that symptoms require treatment, the recommended treatment algorithm for bleeding episodes is described below:
  1. A single dose can be administered according to the guidelines in Table 4.
  2. The patient should be instructed to re-evaluate symptoms in 24 hours for bleeds treated with FVIII, FIX or aPCC and in 2-3 hours for bleeds treated with rFVIIa.
    - a. Administration of FIX Extended half-life should not be more frequent than every 5-7 days.
  3. If a second dose (in the case of FVIII, FIX or aPCC) or a third dose (in the case of rFVIIa) is needed, the patient must call the study center before dosing.
    - a. Consider evaluation and treatment of the patient at the study center and confirmation of bleeds when any repeated doses are needed (See Section 6.4 and Table 2).
    - b. If more than two doses of FVIII, FIX or aPCC or three doses of rFVIIa are needed, the patient should be seen at the study center within 48-72 hours.
  4. Doses should not be administered at less than 24 hour intervals (except rFVIIa as indicated in Table 4).

5. Doses should not exceed the protocol maximum recommended dose indicated in [Table 4](#).
6. Consultation with the study Medical Monitor and Clinical Advisor should be considered for clinical circumstances below, that may warrant AT replacement:
  - a. Doses of factor or BPA higher than those recommended in [Table 4](#)
  - b. Dosing of factor or BPA at decreased intervals than those recommended in [Table 4](#)
  - c. Multiple or repeated doses of factor or BPA
7. Antifibrinolytics may not be used in combination with factor or BPA.

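### SAP 6.3.3.7 counts Day 8 as a standard-BPA day and starts the compliance summary after it, whereas the protocol starts the reduced-BPA guideline on Day 8 (minor)

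*SAP*

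**What the plan says.** SAP 6.3.3.7 plans two summaries that depend on when the fitusiran arm changes BPA dosing. For the standard regimen it says "BPA consumption during Day 1 to Day 8 period under 'standard BPA regimen' will be summarized as appropriate", and it defines the window: "Day 1 to Day 8 period is from Day 1 to the earlier of Day 8 and the last day of bleeding follow up". For adherence to the reduced-dose rules it says "The compliance to the bleed management guideline will be summarized after Day 8 to the end of study".

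Protocol 6.3.1.2 sets the change by study day. The standard-dose instructions are headed "Bleed Management Guidelines Day 1 to Day 7" and the reduced-dose instructions "Bleed Management Guidelines Day 8 and Beyond". The text leading up to them calls for "institution of the protocol-specific bleed management guidelines with reduced BPA at Day 8 and beyond". The patient's paperwork follows the same split: "Patients on fitusiran will be provided a written bleed management plan with appropriate dosing of BPA for use during Day 1 through 7", with a second plan for Day 8 onwards. Among the rules that begin on Day 8 is "Doses should not exceed the protocol maximum recommended dose", which points to the limits in Table 4.

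**The concern.** The SAP's window definition, its label and the start of its compliance summary all put Day 8 on the standard side. The protocol puts it on the reduced side. Two things follow for the fitusiran arm. Doses given on Day 8 under the reduced plan are mixed into a table labelled as standard-regimen use. A Day 8 dose above the Table 4 maximum cannot appear as non-compliance, because the compliance summary has not yet begun.

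The boundary has a safety purpose. Protocol 6.3.1.2 bases it on antithrombin kinetics: by about a week after the first dose, most patients are at or below 60% residual activity. Protocol 1.5 warns that BPA doses above those recommended may raise the risk of thrombosis. A summary of adherence to the dose limits should therefore include the first day on which they apply.

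**Working it through.** The plan states no figure to reproduce here. The check is whether the two documents count days alike, which days differ, and how much could fall on them.

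**Same day count**
- Protocol 6.2.2 starts fitusiran dosing on Day 1.
- SAP 5.2 numbers study days from the Day 1 visit, or from the first dose if that is later, and has no Day 0.
- Protocol Table 8 places Day 8 at 168 h after the Day 1 dose, and (8 − 1) × 24 = 168. The scales agree.

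**End day included**
- SAP 6.3 uses the same construction for the onset period, which ends at the earlier of Day 28 and the end of bleeding follow-up, and describes that period as the first 28 days. Days 1 to 28 number 28 only if the last day is included. By the same reading, Day 8 is inside the standard window.

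**Windows compared**

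| | SAP 6.3.3.7 | Protocol 6.3.1.2 | Difference |
|---|---|---|---|
| Standard regimen | Days 1–8 (8 days) | Days 1–7 (7 days) | Day 8 |
| Reduced-BPA guideline, to Day 246 | Days 9–246 (238 days) | Days 8–246 (239 days) | Day 8 |
| Reduced-BPA guideline, to Day 253 | Days 9–253 (245 days) | Days 8–253 (246 days) | Day 8 |

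Day 246 is the end of the efficacy period. Day 253 is the target day of the end-of-study visit (SAP 5.10) and is closer to the SAP's stated end point for compliance.

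**Share of each window**
- Standard window: 1/8 = 12.5%.
- Guideline window: 1/239 = 0.42%, or 1/246 = 0.41%.

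**Expected treated bleeds starting on Day 8**

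Inputs: 36 fitusiran patients (Protocol 1.3) and the planning ABRs of 4 and 18 (SAP 5.1). The documents give no rate for Day 8. The two planning rates are used as an assumed range, held constant over time.

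Expected number = patients × ABR / 365.25
- ABR 4: 36 × 4 / 365.25 = 0.39
- ABR 18: 36 × 18 / 365.25 = 1.77

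These are bleeds that start on Day 8. Repeat doses given on Day 8 for a bleed that began earlier are not included.

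**The case against.** The best defence is that Day 8 is a boundary day. Protocol 6.3.1.2 also describes the standard regimen as lasting seven days from the start of dosing, and 168 h after the first dose falls on Day 8. A dose on the morning of Day 8 can therefore lie within seven elapsed days. This may well be how the SAP's cut-off arose. It does not reconcile the documents, because the protocol assigns Day 8 by name to the reduced plan in its text, its headings and the written plans. SAP 2.5 and 2.6 list no intended change. They cover only major changes, so their silence is not proof, but nothing suggests that a choice was made.

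The objection on importance stands. The endpoint is exploratory, Protocol 8.2.5.3 leaves its analysis to the SAP, and the standard-window summary is to be made only where appropriate. The bleed guidance is itself a recommendation subject to investigator discretion (Protocol 4.1). Day 8 doses remain in the consumption summaries by study period.

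Two stronger readings are tempting, and the documents support neither.
- A reader might infer that patients could be given standard doses a day too long. Dosing follows the written plans, and the eDiary alert for doses above the patient's plan (Protocol 7.2.1) does not depend on the SAP.
- A reader might take the chance that a bleed starts on Day 8 as the chance that the tables change. The summaries count doses, not bleed starts. A repeat dose for an earlier bleed also changes them, and so does an annualized denominator of 7 rather than 8 days. The number of Day 8 doses that breach the guideline cannot be estimated, because no breach rate is given.

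**Conclusion.** The inconsistency is real and minor. SAP 6.3.3.7 puts Day 8 under the wrong regimen for fitusiran patients and leaves it out of the compliance summary. That conclusion rests only on the wording and the shared day count, not on any assumed rate. The on-demand arm has no change of regimen, so its classification is not at issue.

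The extent is a single day: 12.5% of the short standard window, where it could be visible, and about 0.4% of the long guideline window, where it will hardly show. The estimate of 0.4 to 1.8 bleeds starting that day depends on 36 patients and a constant rate between the two planning ABRs, and it is not a count of doses. No primary or secondary endpoint, alpha, power or dosing instruction is touched.

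**What to change.** In SAP 6.3.3.7, make two changes:
- Define the standard-regimen window as Day 1 to the earlier of Day 7 and the last day of bleeding follow-up, and relabel the period to match.
- Summarize compliance with the bleed management guideline from Day 8 to the end of study.

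The cost is wording and one programmed cut-off moved by a day. No new data are needed, no confirmatory analysis changes, and the protocol needs no amendment.
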